10.0 Study Timelines

10.1 Describe the anticipated duration needed to enroll all study subjects.

Response:

It is anticipated that all participants will be enrolled within two years of the start of the study.

10.2 Describe the duration of an individual subject's participation in the study. Include length of study visits, and overall study follow-up time.

Response:

Aim 1: Participants will come to Kimball Tower on South Campus three times for approximately 1 hour each session.

Aim 2: Participants with stroke will be asked to come to Kimball Tower a total of 4 times (2 pre-tests and 2 post-tests) and participate in a 10 week in-home technology guided exercise program. Pre and post testing will be done in the two weeks pre and post the exercise program. The caregiver feedback measures would obtain information from caregivers in one session lasting 5-30 minutes depending on the amount of feedback the caregiver provides. We could conduct the interview over the phone on or near the last day of the testing session or the caregiver can do it in person during the participant's 3rd or 4th testing sessions.

10.3 Describe the estimated duration for the investigators to complete this study (i.e. all data is collected and all analyses have been completed).

Response:

It is anticipated that data collection and analyses will be completed in 2-2.5 years.

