16.0 Data Management and Analysis

16.1 Describe the data analysis plan, including any statistical procedures. This section applies to both quantitative and qualitative analysis.

Response:

Aim 1:

Validation of smartphone with motion monitor system. We will look at consistency of motor performance across time.

Aim 2:

A strength of the proposed single-subject study design is the internal validity gained by using repeated measurement from the same individuals and the ability to replicate the effect of the intervention across participants. As is typical with single-subject designs, visual inspection will be used as the first stage of analysis to determine the general stability of performance during the baseline phase and the trend of performance change during the training intervention. Statistical analysis to corroborate the visual analysis will include time-series analysis to infer changes in trend and level across phases.⁸⁰ The serial dependency in the data for each participant will be accounted for using the autoregressive integrated moving average (ARIMA).⁸⁰ If a significant positive trend in overall performance during the training intervention is observed, the hypothesis will be accepted. To validate the effect of the training program on the performance measures, the effect on the standardized assessments will be tested. A repeated measures analysis of variance (ANOVA) will be used to assess whether there is a difference within each participant for performance on the Wolf

Motor and 9 hole peg test assessments at the start of baseline, end of baseline, start of follow-up, and end of follow-up. Post hoc pairwise comparisons will be used to assess the differences $\Delta B = B_{end} - B_{start}$, $\Delta T = F_{start} - B_{end}$, and $\Delta F = F_{end} - F_{start}$. It is hypothesized that ΔB and ΔF will be 0, indicating stable performance during the baseline and follow-up, and that $\Delta T > 0$. If these results are consistent with the findings from the functional tests, then the results will be considered valid.

16.2 If applicable, provide a power analysis.

NOTE: This may not apply to certain types of studies, including chart/records reviews, survey studies, or observational studies. This question is asked to elicit whether the investigator has an adequate sample size to achieve the study objectives and justify a conclusion.

Response:

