Aim 1: In a study (N=15 young adults) we will examine the ability of the smartphone to accurately identify the above listed components for the ADLs listed in Table 1. Each participant will be asked to perform five repetitions of each activity in three different testing sessions. We will qualify the performance of our activity recognition algorithms using accuracy and area under the receiver-operator characteristic (ROC) curve (AUC). We will perform an evaluation with random hold out and cross-validation as well as leave-one-person-out evaluation. Particularly, we will compute sensitivity, specificity, and F-measure values. Then we will generate a learning curve that plots classification accuracy as a function of training set size and will add data collection time until the curve plateaus. Our previous research work has shown that it is critical to collect enough sensor training data in building robust models. Similarly, we will consider recruiting new participants until the curve plateaus.

Aim 2: Sample size estimation was based on the repeated measures ANOVA test of within subjects change in standardized assessment scores from baseline to follow-up. With $\alpha = 0.05$, power = 0.8, 4 measurements, and a desired effect size (f) = 0.25 to detect, a sample size of 15 participants is needed. This effect size is consistent with studies on functional activity performance and recovery following stroke.⁶⁸ A total of 20 participants will be recruiting to account for a 25% attrition rate.

16.3 Describe any procedures that will be used for quality control of collected data.

Validation of the system in aim 1 acts as a quality control.

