19.0 Withdrawal of Subjects

N/A: This study is not enrolling subjects. This section does not apply.

19.1 Describe anticipated circumstances under which subjects may be withdrawn from the research without their consent.

Response: If participants fail to complete the testing sessions in Aim 1 in a timely manner, they may be withdrawn from the study.

Participants will be assessed with the Berg Balance Scale. If they do not score above a 42, they will only perform exercises in a seated position in Aim2. If participants report pain with activities in the program and the program cannot be modified to eliminate pain, the participant will be taken out of the study.

19.2 Describe any procedures for orderly termination.

NOTE: Examples may include return of study drug, exit interview with clinician. Include whether additional follow up is recommended for safety reasons for physical or emotional health.

Response: Exit interview with research personnel. If balance concerns have prompted termination in the training portion of the study, the PI will consult with the participant. The participant will need to return the rehabilitation device and fill out the paper work for payment of the pre-intervention testing session.

19.3 Describe procedures that will be followed when subjects withdraw from the research, including retention of already collected data, and partial withdrawal from procedures with continued data collection, as applicable.

Response:

Data collected prior to participant's departure from the study may be used in portions of the data analyses.

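### Repeated measures ANOVA on the standardized assessments has no plan for missing visits despite 25% expected attrition, so the training contrast ΔT can be biased if leaving is related to performance

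*Combined protocol and SAP*

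**What the plan says.** Section 16.1 (Aim 2) names the method for the Wolf Motor and 9-hole peg tests: "A repeated measures analysis of variance (ANOVA) will be used to assess whether there is a difference within each participant". The time points are "assessments at the start of baseline, end of baseline, start of follow-up, and end of follow-up". It continues: "Post hoc pairwise comparisons will be used to assess the differences", namely ΔB (change over baseline), ΔT (start of follow-up minus end of baseline) and ΔF (change over follow-up). ΔT carries the training effect. Section 10.2 has stroke participants attend "a total of 4 times (2 pre-tests and 2 post-tests").

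The sample size in section 16.2 rests on the same ANOVA, with "power = 0.8, 4 measurements, and a desired effect size (f) = 0.25 to detect". It gives 15 participants, and then: "A total of 20 participants will be recruiting to account for a 25% attrition rate".

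On incomplete participants there is one sentence, in section 19.3: data collected before a participant's "departure from the study may be used in portions of the data analyses". It does not say which analyses or how. No section defines an analysis population, a rule for missed visits, imputation, a mixed model or a sensitivity analysis.

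The ANOVA does not decide Aim 2. Section 16.1 accepts the hypothesis on the trend in the smartphone measures during training, by visual inspection and ARIMA within each participant. The standardized assessments are there to corroborate it.

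**The concern.** A classical repeated measures ANOVA needs all four values from each person. That is a property of the method; the protocol does not write down any deletion, but it names no alternative. Someone who leaves during training has the two pre-tests only. They drop out of the omnibus test, and they cannot enter a paired ΔT either.

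This is harmless if leaving has nothing to do with performance. The plan gives reason to doubt that. Section 19.1 takes out participants whose pain cannot be removed by modifying the program, section 3.0 asks those with increased pain to stop the training tasks, and the training is done at home. Ability or response to training may therefore differ between those who stay and those who leave. There is no control group in which a similar shift could offset it.

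What is at stake is ΔT on the two clinical tests: the corroboration of the smartphone result, and the analysis on which the sample size was built.

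**Working it through.** **1. The plan's own figures (section 16.2).**

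- Recruited N: 15 / (1 − 0.25) = 20. This reproduces exactly, so the plan expects about 15 complete participants and about 5 lost.
- The 15: for a one-group within-subject F test, λ = f²·n·m / (1 − ρ), with 3 and 3(n − 1) degrees of freedom and sphericity assumed. The plan gives f = 0.25 and m = 4 but no correlation ρ. At ρ = 0.7, λ = 0.0625 × 15 × 4 / 0.3 = 12.5 and power is 0.82, with 15 the smallest N that reaches 0.80. At ρ = 0.5, λ = 7.5, power is 0.58, and 24 would be needed. So 0.7 is the value nearest the plan's own N. I use 0.7 and, for range, 0.5.

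**2. Who can contribute.**

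| Visits observed | Omnibus ANOVA | Separate paired ΔB | Separate paired ΔT |
|---|---|---|---|
| All four | yes | yes | yes |
| Missing the last only | no | yes | yes |
| Two pre-tests only | no | yes | no |

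**3. Bias when leaving depends on the end-of-baseline score.** None of these inputs is in the documents; they are assumptions. Scores have SD 1 and are coded so that higher is better (a timed test must be reversed). Any two visits correlate at ρ, the true ΔT is 0.50 SD, and 25% leave before the post-tests.

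Let z be the end-of-baseline score, with P(leave | z) = 1 / (1 + exp(−(a − s·z))). The constant a is set so that 25% leave: a = −1.16, −1.31 and −1.78 for s = 0.5, 1 and 2. Since E[F_start | z] = 0.50 + ρz,

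bias among completers = −(1 − ρ) × E[z | stay].

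Numerical integration gives E[z | stay]:

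| Odds ratio per SD (e^s) | E[z given stay] | Bias, ρ = 0.7 | Bias, ρ = 0.5 |
|---|---|---|---|
| 1.65 | 0.120 | −0.3 × 0.120 = −0.04 | −0.5 × 0.120 = −0.06 |
| 2.72 | 0.213 | −0.06 | −0.11 |
| 7.39 | 0.319 | −0.10 | −0.16 |

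Against 0.50 this is an understatement of 7 to 19% at ρ = 0.7 and 12 to 32% at ρ = 0.5. If better performers leave more often, s changes sign and so does the bias. If leaving is unrelated to performance, the bias is zero.

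**4. What a likelihood analysis does.** I ran 20,000 simulated trials of 20 participants per scenario. The likelihood estimate regresses F_start on both baseline scores and evaluates the fit at the baseline means of everyone enrolled. In all scenarios of step 3 it averaged 0.50. Its standard error was similar to that of completers: 0.20 for both at ρ = 0.7, odds ratio 1.65, and 0.27 against 0.25 at ρ = 0.5, odds ratio 7.39.

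**5. When leaving depends on the unobserved training gain.** Smaller gains make leaving more likely; the truth is again 0.50.

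| Odds ratio per SD | Completers, ρ = 0.5 / 0.7 | Likelihood, ρ = 0.5 / 0.7 |
|---|---|---|
| 1.65 | 0.62 / 0.59 | 0.58 / 0.57 |
| 2.72 | 0.71 / 0.67 | 0.65 / 0.62 |

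Here completers overstate ΔT, and the likelihood analysis removes only about 30% of the excess.

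**The case against.** Several points on the other side are sound.

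- **Reach.** A reader might infer that the main Aim 2 result rests on completers only. The documents do not support that. The hypothesis is accepted on the smartphone trend, analysed within each participant, so a person who leaves mid-training still contributes baseline data and part of the training series.
- **Section 19.3.** A reader might see a contradiction between its permission to use earlier data and an ANOVA that cannot use them. It speaks only of portions of the analyses. Using those data in the smartphone series and in ΔB fits that wording, so the rule is unspecified, not contradicted.
- **Deletion.** It would be too strong to say that anyone missing one visit is lost everywhere. If the planned pairwise comparisons are run as separate paired contrasts, someone missing only the last visit still gives ΔT. The loss that remains is the participant with pre-tests only.
- **Size.** The upper figures need very strong dropout (odds ratio 7.4 per SD), for which the documents offer nothing, and the largest also needs correlation 0.5 where the planned N points to about 0.7. Every bias in step 3 is smaller than the standard error of a single trial (0.20 to 0.26 SD for completers). If poorer performers leave, the completer estimate is conservative.
- **Remedy.** The mixed model is not a cure for every kind of dropout. Pain arises during training, after the last pre-test, so observed scores may not capture it. Step 5 shows what then remains.

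These points limit the claim. They do not supply a rule for missing visits or a way for mid-training leavers to inform ΔT.

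**Conclusion.** The point holds for the standardized assessments. The plan expects to lose about 5 of 20 participants, specifies an ANOVA whose omnibus test uses complete participants only, and states no handling of missing visits. Participants who leave during training cannot inform ΔT, which can therefore be biased if leaving is related to performance.

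That the handling is missing is certain. The size and direction of any bias are not: they depend on a dropout mechanism and a correlation that the documents do not give. On the assumptions above, with poorer performers leaving, ΔT is understated by about 0.04 to 0.10 SD at correlation 0.7 and 0.06 to 0.16 SD at 0.5. With better performers, or those with the smallest gains, leaving, it is overstated. A reader might infer that the plan inflates the training effect; the documents do not settle the direction. Because the ANOVA corroborates rather than decides Aim 2, this is a change that should be made, not one that undermines the trial.

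**What to change.** Replace the ANOVA in section 16.1 with a linear mixed model fitted by REML to everyone with at least one assessment:

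- visit as a four-level factor, with ΔB, ΔT and ΔF tested as contrasts;
- Kenward-Roger degrees of freedom;
- a covariance fixed in advance: unstructured, with one named fallback (for example compound symmetry) if it does not converge. An unstructured 4 × 4 matrix has 10 parameters, a lot for about 15 complete participants, so the fallback should not be left open until the data are seen.

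Under the unstructured covariance, sphericity is no longer assumed. State the analysis population, and have section 19.3 name the analyses that use data from participants who leave.

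The model removes the bias only if dropout depends on observed scores. So record the reason for every withdrawal, and add one pre-specified sensitivity analysis for dropout related to response, for example imputing post-test values for leavers under no training gain.

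The cost is wording and slightly more analysis work, plus a field for withdrawal reasons. No visit or outcome measure is added and N is unchanged. Under strong dropout the standard error of ΔT may be larger by up to about 0.03 SD.

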Aim 2: Examine performance changes in trained ADLs when augmenting 3D printed objects with smart technology to provide quantitative feedback on performance. Study Design: A single-subject experimental design with a multiple baseline, multiple probe testing setup is well suited to stroke rehabilitation research. With inherent variability between motor performance of individuals with stroke, there is an advantage to having participants serve as their own control. The level of stability of motor performance will be established during baseline by three different assessments (described in “Assessments” below). Each participant will have a varying length of the baseline period to establish that the intervention, rather than time, is the primary reason for any observed change in performance. For the intervention, all participants will be asked to complete a six-week in home training program as described in “Training Intervention” below. A follow-up phase, using the same assessments as in the baseline, will be repeated for the purpose of assessing carry-over post intervention. Training Intervention: Training will focus on upper extremity ADLs and manipulating or transporting the 3D printed objects instrumented with a smartphone, the smartphone will be supplied for the length of the training program (Table 1 in attached grant proposal). Participants will be cued to start their rehabilitation program by setting an alarm on the smartphone. The smartphone will be placed either in (e.g., the bowl) or on (e.g., the key) the 3D printed device. During the initial assessment, rehabilitation professionals will work with participants to determine which tasks can be completed safely. Task modifications will be made as necessary to protect joint integrity and balance. Similar to previous research in stroke, training will be tailored to the participant’s ability. The majority of training ADLs give participants the opportunity to perform them in a seated position. However, some participants may prefer to stand as this position is more functional for many of the ADLs. Participants will be asked to complete a minimum of 10 repetitions of each task they are training once a day/ five days per week for six weeks. These common ADLs include general arm movement (horizontal transport), forearm pronation and supination (pouring) and fine motor (key). Participants will receive auditory feedback on count or speed of movement in real time. Feedback will be given as described previously. The goal is to perform tasks more smoothly and in less time than the previous session. If participants have increased pain with training, they will be asked to stop doing the training tasks and contact the PI.

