9.0 Procedures Involved

9.1 Provide a description of **all research procedures or activities** being performed and when they are performed once a subject is screened and determined to be eligible. Provide as much detail as possible.

NOTE: This should serve as a blueprint for your study and include enough detail so that another investigator could pick up your protocol and replicate the research. For studies that have multiple or complex visits or procedures, consider the addition of a schedule of events table in in your response.

Approach: Our goal is to develop portable technology capable of cueing a home training program, collecting data on upper limb motor performance and providing user feedback on performance.

Response: Aim 1: Participants will be asked to come to Kimball Tower three times within a two week time span to demonstrate consistency of motor performance. An infrared motion monitor system will be used to track their movement and compare kinematics produced by the smartphone with kinematics produced from the infrared motion monitor system. Participants may be video taped during data collection to further assess mobility.

Aim 2

Wolf Motor Function Test (WMFT): examines functional abilities. It is a valid and reliable outcome measure following stroke

9-Hole Peg Test: a timed test of manual dexterity which involves lifting/placing/removing 9 pegs into/out of holes. It is both valid and reliable in measuring arm function after stroke.

Grip assessment: Grip strength is measured with a hand dynamometer.

Berg Balance Scale: A 14-item scale designed to measure balance

All clinical assessments are recommended Outcome Measures by the APTA for stroke (<http://www.neuropt.org/professionalresources/neurology-section-outcome-measures-recommendations/stroke>)

Use of smartphone and 3D printed objects will be in home over a 11- week span. Five of these weeks the participants will perform a limited number of task trials without feedback to act as a probe for performance quality. The other 6 weeks, participants will be asked to perform their exercise program 5/7 days and the in home exercise program may take up to an hour to complete.

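### The Aim 2 check on the clinical tests prints a sign that is reversed for raw 9-Hole Peg Test time, and gives no criterion for a change being zero

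*Combined protocol and SAP*

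**What the plan says.** Section 16.1 has two layers for Aim 2. The first is the smartphone data on the trained tasks: "If a significant positive trend in overall performance during the training intervention is observed, the hypothesis will be accepted". The second is a repeated measures ANOVA on the Wolf Motor and 9-Hole Peg tests at four time points: start and end of baseline, and start and end of follow-up. Within that second layer, "Post hoc pairwise comparisons will be used to assess the differences" over baseline (end minus start), over training (start of follow-up minus end of baseline) and over follow-up (end minus start). The plan expects that the baseline and follow-up changes "will be 0, indicating stable performance during the baseline and follow-up, and that" the training change exceeds 0. One rule covers both tests. Agreement between the two layers then carries weight: "If these results are consistent with the findings from the functional tests, then the results will be considered valid".

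On the scores themselves, section 9.1 gives "9-Hole Peg Test: a timed test of manual dexterity which involves lifting/placing/removing 9 pegs into/out of holes", and section 9.2 repeats the description. The Wolf Motor test is described only as examining functional abilities, and the score to be analysed is not named.

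On stability, section 16.1 says that "visual inspection will be used as the first stage of analysis to determine the general stability of performance during the baseline phase". Section 3.1 adds: "The level of stability of motor performance will be established during baseline by three different assessments". Neither statement gives a threshold.

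**The concern.** There are two gaps in the same check.

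**Direction.** A single rule that the training change should exceed 0 fits a score that rises with improvement. A completion time falls with improvement. No section says that times are inverted, recoded or scored so that higher is better. Taken literally, a participant who becomes faster on the peg test contradicts the stated expectation, and one who becomes slower meets it. For the Wolf Motor test the correct sign cannot be worked out, because the score is not named.

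**Stability.** The check expects two changes to be zero but does not say what result would count as zero. For the clinical tests, post hoc pairwise comparisons are the only tool named. If a non-significant comparison were taken as stability, a real drift on these tests could be reported as no change, and the training change would then be read against that description.

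**Working it through.** **Direction.** The training change is F_start − B_end. If the peg test is recorded as time and the participant improves, then time at F_start is less than time at B_end, so F_start − B_end < 0. The plan prints > 0. The two agree only if the score is reoriented first, and sections 9.1, 9.2 and 16.1 state no such step. No one-sided test is stated. The estimate, its interval and a two-sided p-value are therefore the same whichever sign is expected; only the reading against the expectation changes.

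**The plan's own sample size.** Section 16.2 gives alpha 0.05, power 0.8, 4 measurements, f = 0.25 and N = 15, with 20 recruited for 25% attrition. The attrition step reproduces: 15/(1 − 0.25) = 20. N = 15 depends on a between-visit correlation ρ that the documents do not give. For a one-group repeated measures ANOVA with sphericity assumed, λ = f² × n × m/(1 − ρ), with df 3 and 3(n − 1). At ρ = 0.7 and n = 15, λ = 0.0625 × 15 × 4/0.3 = 12.5 and power is 0.819; at n = 14 power is 0.785. So 15 is the smallest sufficient N at ρ = 0.7, and more generally for ρ of about 0.687 to 0.709. That is the reason for using 0.7 as the central assumption below. It does not show that 0.7 is the true value.

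**Precision of a change over baseline or follow-up.** Let SD be the between-person SD at one visit.

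- SD of a paired change = √(2(1 − ρ)) SD. At ρ = 0.7 this is √0.6 = 0.775 SD.
- 95% CI half-width = t(0.975, n − 1) × SD of change/√n.
- n = 15: 2.145 × 0.775/3.873 = 0.43 SD.
- n = 20: 2.093 × 0.775/4.472 = 0.36 SD.

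**Chance that a real drift is non-significant.** Noncentral t, two-sided 0.05, unadjusted, with noncentrality (drift/SD of change) × √n. For a drift of 0.25 SD at ρ = 0.7 and n = 15 this is (0.25/0.775) × 3.873 = 1.25, which gives 0.786. Each cell below shows n = 15 / n = 20.

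| Assumed ρ | CI half-width (SD) | 0.25 SD drift missed | 0.5 SD drift missed |
|---|---|---|---|
| 0.6 | 0.50 / 0.42 | 83% / 78% | 48% / 34% |
| 0.7 | 0.43 / 0.36 | 79% / 72% | 36% / 22% |
| 0.8 | 0.35 / 0.30 | 70% / 61% | 19% / 8% |
| 0.9 | 0.25 / 0.21 | 48% / 34% | 2% / 0.3% |

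The plan states no multiplicity adjustment. With Bonferroni for the three contrasts, a 0.25 SD drift at ρ = 0.7 would be missed 90% / 85% of the time (0.897 / 0.855).

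**The case against.** The best defence on direction is that section 16.1 speaks throughout of performance, and that positive there means better. Its trend rule already asks for a positive trend, yet the measures named for the trained tasks are completion time and normalized jerk score. Both fall with improvement, and section 3.1 sets the aim accordingly: "The goal is to perform tasks more smoothly and in less time than the previous session". This stands as the probable intent. It does not repair the formula, which is an explicit subtraction of scores with no orientation stated.

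A reader might infer that a working programme would be declared a failure on a significance test. The documents do not support that, because no one-sided test of the printed sign is planned.

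On stability, a reader might infer that the plan treats a non-significant comparison as proof of no change. It does not say so; it states an expectation and leaves the criterion open. Nor is the follow-up phase otherwise unexamined. Section 3.1 repeats the baseline assessments to look at carry-over, section 9.2 schedules probes in each follow-up week, and section 16.1 plans time-series analysis across phases. But the probes and the time-series analysis concern the trained tasks, and none of these supplies a criterion for the clinical tests.

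It would also be too strong to say that 15 to 20 people cannot show stability. At a correlation of 0.9, a 0.5 SD drift would nearly always be detected.

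**Conclusion.** The point holds and is minor. For raw peg-test time the printed expectation has the wrong sign. For the Wolf Motor test the sign cannot be determined from the documents. What is affected is the yardstick for calling results valid, and not the estimates, intervals or two-sided p-values.

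The stability part is conditional. If non-significance were read as stability on the clinical tests, the evidence would be weak with 15 to 20 people unless the correlation between visits is high. The figures rest on assumed correlations and drift sizes, which the documents do not give, and on equal SDs across visits. The problem is large for small drifts and shrinks as correlation or drift rises.

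A reader might go on to infer that the Aim 2 conclusion itself is unsafe. The documents do not support that on this ground. The hypothesis is accepted on the smartphone trend, and section 3.1 varies the baseline length between participants as a separate guard against time effects.

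**What to change.** In section 16.1:

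1. State the expected training change as below 0 for 9-Hole Peg Test time and for any timed Wolf Motor score, and above 0 for scores where higher is better. Alternatively, define every change so that positive means improvement. Either wording requires naming the Wolf Motor score analysed.
2. Report the baseline and follow-up changes on the clinical tests with 95% confidence intervals, and describe stability from those intervals and not from a non-significant comparison. This does not need an equivalence margin.

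The cost is a few sentences, with no added data or participants. The downside is that the intervals will be wide. At correlation 0.7 the full width is about 2 × 0.43 = 0.86 SD with 15 people and 2 × 0.363 = 0.73 SD with 20, so stability on the clinical tests may often have to be described as uncertain.

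### The clinical-test check in Aim 2 never compares the change over training with the change over baseline, so retest practice or slow drift can pass as corroboration of a training effect

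*Combined protocol and SAP*

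**What the plan says.** Section 16.1 of the combined protocol and SAP has two strands for Aim 2. The first covers the smartphone performance measures: visual inspection, then a time-series (ARIMA) analysis of trend and level across phases. The Aim 2 hypothesis is accepted on the trend during training.

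The second strand is meant to validate that result on the Wolf Motor and 9-hole peg tests. Scores at four occasions (start and end of baseline, start and end of follow-up) go into a repeated measures ANOVA. Then "Post hoc pairwise comparisons will be used to assess the differences": ΔB over baseline, ΔT from the end of baseline to the start of follow-up, and ΔF over follow-up. ΔB and ΔF are hypothesized to be zero, "indicating stable performance during the baseline and follow-up", and ΔT to be above zero. The section concludes: "If these results are consistent with the findings from the functional tests, then the results will be considered valid". It gives no margin or confidence interval for stability, no contrast of ΔT with ΔB, and no term for weeks.

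There is no control group. Section 3.1 relies on a staggered baseline instead: "Each participant will have a varying length of the baseline period to establish that the intervention, rather than time, is the primary reason". Section 16.2 sizes Aim 2 on the ANOVA: "Sample size estimation was based on the repeated measures ANOVA test of within subjects change in standardized assessment scores", with "4 measurements, and a desired effect size (f) = 0.25 to detect". From this "a sample size of 15 participants is needed", and 20 are recruited "to account for a 25% attrition rate".

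**The concern.** A ΔT that differs from zero beside a ΔB that does not is no evidence that ΔT exceeds ΔB. The two changes have to be compared directly. A non-significant ΔB from 15 people also says little about stability, because a sizeable baseline change would often be missed.

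Spacing can make this worse. ΔT covers at least the six training weeks. Section 9.1 gives five non-training weeks, which section 9.2 divides between baseline and follow-up without saying how. If baseline is the shorter interval, the same weekly drift is easier to detect in ΔT than in ΔB. The stagger exists to separate training from time, but the four-occasion analysis does not use it.

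At stake is whether the clinical tests can be said to support training as the cause, rather than repeated testing or time.

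**Working it through.** **Inputs from the documents.** α = 0.05 (sidedness not stated; two-sided assumed), power 0.80, m = 4 measurements, f = 0.25, n = 15 (section 16.2); six training weeks (section 3.1).

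**Assumptions, not in the documents.** Equal correlation ρ between occasions, changes in units of the between-person SD with improvement positive, test weeks 0, 2.5, 8.5 and 11 unless stated, and the drift and retest sizes below.

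**1. The plan's own figure.** For a one-group within-subject ANOVA, λ = f²·N·m/(1 − ρ) with 3 and 3(N − 1) degrees of freedom. At ρ = 0.7, λ = 0.0625 × 15 × 4 / 0.3 = 12.5, power is 82%, and 15 is the smallest N reaching 80%. At ρ = 0.5 the formula needs 24 and at ρ = 0 it needs 45. The stated 15 therefore implies ρ of about 0.7, which I take as the lower end of the range, with 0.9 as the upper. Attrition: 15/(1 − 0.25) = 20, as stated.

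**2. What a non-significant ΔB shows.** The 95% half-width for a single change is t(14)·√(2(1 − ρ)/15), with t(14) = 2.145.
- ρ = 0.7: 2.145 × √(0.6/15) = 0.43 SD
- ρ = 0.9: 2.145 × √(0.2/15) = 0.25 SD

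At ρ = 0.7 a true baseline change of 0.3 SD is missed 71% of the time. One of 0.5 SD is missed 36% of the time. That is the step implied by f = 0.25: two occasions at 0 and two at d have a standard deviation of d/2, so d = 0.5.

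**3. How often the pattern appears with no training effect.** Simulation with n = 15 and one outcome. The pattern is ΔT significantly above zero with ΔB and ΔF not significant. Ranges run across the stated gains or drifts.

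| Scenario | ρ = 0.7 | ρ = 0.8 | ρ = 0.9 |
|---|---|---|---|
| No drift, no practice | 2% | 2% | 2% |
| Equal gain per retest, 0.15–0.25 SD | 10–18% | 13–22% | 18–22% |
| Gain halves at each retest, first 0.15–0.25 SD | 5–8% | 5–9% | 8–12% |
| Drift 0.03–0.05 SD/week, 2.5-week baseline | 12–26% | 16–36% | 28–53% |
| Same drift, 5-week baseline, 2-week follow-up | 12–25% | 16–32% | 27–35% |

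With Bonferroni over the three changes, the equal-gain row becomes 4–10%, 6–14% and 11–21%, and the 2.5-week drift row 6–14%, 8–22% and 16–44%. The adjustment lowers most settings but not all. At ρ = 0.9 and gain 0.25 the rate goes from 18% to 21%, because the stricter threshold also makes ΔB and ΔF less likely to be flagged.

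**4. The direct contrast.** ΔT − ΔB = F_start − 2·B_end + B_start has variance (1 + 4 + 1)(1 − ρ) per person, so its half-width is t(14)·√(6(1 − ρ)/15).
- ρ = 0.7: 2.145 × √(1.8/15) = 0.74 SD
- ρ = 0.9: 2.145 × √(0.6/15) = 0.43 SD

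Under equal retest gains its expectation is g − g = 0, and it rejects in the improving direction in about 2.5% of studies. Under drift w per week its expectation is 6w − 2.5w = 3.5w, and it rejects in about 5 to 13%. It removes equal practice but only part of drift.

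**5. A model with participant, weeks and a post-training step.** It removes linear drift (about 2.5% false positives). Under equal retest gains g, however, the within-phase slope is g/2.5 = 0.4g per week. Six weeks then predict 2.4g against an actual ΔT of g, so the step is biased by g − 2.4g = −1.4g. With baselines staggered over 1 to 4 weeks the bias is about −0.9g. For g = 0.15 to 0.25 SD, −1.4g is −0.21 to −0.35 SD. The half-width is about 0.93 to 1.01 SD at ρ = 0.7 and 0.54 to 0.58 at ρ = 0.9.

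**The case against.** The strongest objection is to the size. Every rate rests on drift, practice and correlation values that the documents do not give, and the settings are partly unfavourable. Practice that fades shows up early, in ΔB. A longer baseline narrows the gap between intervals: section 24.0 counts all five non-training weeks as baseline, although section 9.2 also has follow-up weeks. The plan says post hoc without naming an adjustment, and an adjustment would lower most rates. The plan also has two clinical tests and asks for consistency with the functional findings; no joint rate was computed. All of this stands, so the rates show what can happen and are not a forecast.

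It is also fair that the plan never says a non-significant result proves stability. That reading is an inference, drawn because pairwise comparison is the only method named for judging whether ΔB and ΔF are zero.

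A reader might infer more than the documents support:
- That drift or practice *will* pass as a training effect. It can; how often depends on unknown quantities.
- That the ANOVA treats visits as interchangeable. It is a within-person analysis of ordered occasions; it ignores their spacing, not their order.
- That the Aim 2 conclusion falls. The hypothesis is accepted on the performance-measure trend, with ARIMA across phases. The clinical tests are a corroborating check.
- That weeks plus a step should carry the attribution. Step 5 shows it is biased under retest practice and less precise than ΔT − ΔB. Staggering over 1 to 4 weeks only moves its half-width from 1.01 to 0.93 SD at ρ = 0.7.

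**Conclusion.** The concern holds in this form. The clinical-test check supports attribution by separate pairwise comparisons. It never estimates whether the change over training exceeds the change over baseline, sets no standard for stability, and leaves the actual weeks unused. With no training effect, under the assumptions in the working and unadjusted tests on one outcome, the supporting pattern appears in roughly 10 to 22% of studies with equal retest gains and about 5 to 12% if gains halve. With drift it appears in 12 to 53%, or up to about 35% with a 5-week baseline. With neither it is about 2%. The defect lies in a secondary, corroborating analysis, but one the plan uses to call its results valid. It should be corrected, and the data needed for the main change are already planned.

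**What to change.** In section 16.1:
- Keep ΔT as the planned test. Report ΔB, ΔT, ΔF and ΔT − ΔB for each clinical test, each with a 95% confidence interval.
- Base the attribution statement on ΔT − ΔB, and state that a non-significant ΔB or ΔF is not evidence of stability.
- State the baseline and follow-up lengths, reconciling the 11-week span in section 9.1, the 10-week program in section 10.2 and the five baseline weeks in section 24.0. Record the actual date of each clinical test.
- As a sensitivity analysis only, fit participant + actual weeks + post-training step. Say that it removes linear drift but is biased downward by retest practice (about −0.9 to −1.4 times the gain per test), while ΔT − ΔB removes equal practice but only part of drift.

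The cost is wording and date recording; no visits or participants are added. The downside is precision. At n = 15 the contrast carries ±0.74 SD at correlation 0.7 (±0.43 at 0.9), and the step about ±0.93 to 1.01 (±0.54 to 0.58), against ±0.43 (±0.25) for ΔT alone. For a true 0.5 SD step at correlation 0.7, ΔT − ΔB has 27% power with 15 participants. Both should be presented as estimates, not pass/fail gates.
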